Objective 3 will be a methodological study to develop and apply methods of quantitative bias analysis to account for potential biases arising in the estimates of the effects of ICS on COVID-19 outcomes.

H. Data source

This project will use the Clinical Practice Research Datalink (CPRD) Aurum, a database containing routinely collected patient data from GPs in the UK. CPRD Aurum includes data on 41 million patients (March 2022), with over 13 million patients currently registered (20% of the UK population).³¹ These patients come from over 1,300 GP practices which use EMIS GP patient management software.³¹ CPRD records information on diagnoses, symptoms, demographics and lifestyle factors, prescriptions, referrals, vaccinations and tests^{31,32}, coded using SNOMED and Dictionary of Medicines and Devices (DM+D) codes. CPRD Aurum has been shown to be broadly representative of the English population in terms of age, gender, geographical spread and deprivation.³²

I. Linked data

Data from CPRD can be linked to other databases such as the Hospital Episode Statistics (HES) and the Office for National Statistics (ONS) death registry. Both HES and ONS death registry data are linked to CPRD by NHS Digital using the NHS number, gender, date of birth and postcode.^{32,33} HES holds information on all patient contacts at NHS hospitals in England, with diagnoses recorded using International Classification of Disease 10th revision (ICD-10) codes.^{33,34} ONS death registry data contains information on all deaths occurring in England and Wales, including a cause of death documented using ICD-10 codes.^{34,35}

HES Admitted Patient Care will be used to identify hospitalisation with COVID-19. ONS death registration data will be used to identify death with COVID-19. Additionally, the Index of Multiple Deprivation (IMD) will be used as a covariate to adjust for socioeconomic deprivation, which has been associated with COVID-19 outcomes.³⁶

J. Feasibility counts

A feasibility count based on CPRD Aurum June 2021 build identified 225,472 patients with a COPD code before 29th February 2020, and 755,632 patients with an asthma code between 1st March 2017 and 29th February 2020. These patients were registered in CPRD on 1st March 2020 and had at least one year of registration prior to that date.

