Furthermore, 1,031,882 patients who received a prescription for ICS between 01st March 2019 and 29th February 2020 were identified. Of the patients with asthma, 485,192 had a prescription for ICS. Of the patients with COPD, 83,668 had a prescription for ICS.

		With ICS prescription 01/03/2019-29/02/2020
Asthma	755,632	485,192 (64.2%)
COPD	225,472	83,668 (37.1%)

K. Sample size considerations

Between 01st March 2020 and 31st August 2020, 295,134 positive SARS-CoV-2 tests were reported in England.³⁷ Based on a population of 56,550,000³⁸, that corresponds to 0.52% of the population testing positive for SARS-CoV-2. During that time period, 36,974 deaths with COVID-19 occurred in England, corresponding to 0.065% of the population.

Table 1. Sample size calculations for $\alpha = 0.05$ and 80% power, assuming 64% of the study population are prescribed ICS.

Outcome probability in controls	HR=1.1	HR=1.2	HR=1.3	HR=1.4	HR=1.5	HR=1.6	HR=1.7
0.05%	7,500,266	2,049,648	989,797	601,807	414,428	308,428	241,978
0.1%	3,750,133	1,024,824	494,899	300,904	207,214	154,214	120,989
0.2%	1,875,067	512,412	247,450	150,452	103,607	77,107	60,495
0.3%	1,250,045	341,608	164,967	100,302	69,072	51,405	40,330
0.4%	937,534	256,206	123,725	75,226	51,804	38,554	30,248
0.5%	750,027	204,965	98,980	60,181	41,443	30,843	24,198
0.6%	625,023	170,804	82,484	50,151	34,536	25,703	20,165
0.7%	535,734	146,404	70,700	42,987	29,602	22,031	17,285
0.8%	468,767	128,103	61,863	37,613	25,902	19,277	15,124
0.9%	416,682	113,870	54,989	33,434	23,024	17,135	13,444
1.0%	375,014	102,483	49,490	30,091	20,722	15,422	12,099

Assuming the probability of testing positive for SARS-CoV-2 among people with asthma or COPD is equal to or higher than the probability of testing positive among the general population, this study will likely be adequately powered to detect HRs of 1.1 or higher in the asthma population and 1.2 or higher in the COPD population for the outcome of testing positive. For the rarest outcome, death, the study would be powered to detect HRs higher than 1.4 in the asthma cohort and 1.7 in the COPD cohort.

L. Study population

Descriptive study

For the descriptive study, we will examine prescription patterns of ICS in two cohorts: patients with COPD and patients with asthma. Follow-up will be from 1st March 2019 until the end of wave 2 of COVID-19 in the UK (30th April 2021).

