For each cohort and each calendar month, the study population will consist of people who have a record of asthma or COPD. For the asthma cohorts, each monthly cohort will consist of those patients who, on the 15th of each month (the index date), had 1) their first asthma code on or before that date; and 2) did not have COPD on or before that date.³⁹ Correspondingly, for the COPD cohorts, each monthly cohort will consist of those patients who, on the 15th of each month, had 1) their first COPD code on or before that date; and 2) did not have asthma on or within 3 years before that date. To be included in a cohort, patients must have at least one year of follow-up in CPRD prior to the index date and have age and gender recorded in CPRD.

Comparative cohort studies

For the comparative cohort studies, the study population will consist of two separate, mutually exclusive disease cohorts, a COPD cohort and an asthma cohort, consisting of patients registered with GP practices meeting CPRD quality control standards. For each disease cohort (asthma and COPD), two cohorts will be created, one for the first wave of COVID-19 and one for the second, defined relative to a cohort entry date (1st March 2020 for wave 1, 1st September 2020 for wave 2), to make a total of four cohorts. To be included in a cohort, patients must have at least one year of follow-up in CPRD prior to the cohort entry date, be eligible for linkage to HES data, and have gender and age recorded in CPRD.

Asthma cohort⁴⁰

The asthma cohort will include all adults aged 18 and over with a recorded diagnosis of asthma defined as a record of asthma within 3 years prior to the cohort entry date. This method of identifying asthma has previously been validated in CPRD.⁴⁰ Code lists to identify asthma will be reviewed by a clinical expert before use.

Patients will be excluded if they have a record of COPD or any other chronic respiratory condition at any point before the cohort entry date, or a prescription of a LAMA but no ICS within 3 years before the cohort entry date, as this indicates possible COPD. Patients who received a prescription of nebulised medication within 1 year before the cohort entry date will also be excluded, as this indicates very severe asthma.

COPD cohort⁴¹

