- Incident ICS exposure will be defined as a new ICS prescription with no prescription in the previous 6 months. Prevalent users will therefore also include incident users.
- The denominator will be all people with asthma or COPD in each month **Error!**

Reference source not found..

- Number of individual prescriptions per person per month (absolute number).
- Dosages prescribed: median or mean daily dose among those prescribed ICS for any given month.
- Discontinuation of ICS or date of treatment switch: number and proportion of people who have ≥ 6 months of no ICS-containing inhaler prescription.

This study will be descriptive. Results will be presented as absolute numbers and proportions as bar graphs.

The results from this study will inform the exposure definition that will be used in the comparative cohort study (see section on Exposure definitions). This study will be completed before starting the analyses for the subsequent comparative cohort studies.

Comparative cohort studies:

We will conduct descriptive analyses (frequency, percentages, mean [SD] and median [IQR]) to assess characteristics of the patients in each cohort, stratified by exposure group at baseline. Categorical variables will be compared using χ^2 tests. Continuous variables will be compared using t-tests for normally distributed variables and Mann-Whitney test for non-normally distributed variables. Time to each outcome will be presented using Kaplan-Meier plots using time in study as the time scale.

Propensity scores will be generated using logistic regression to estimate likelihood of ICS prescription based on baseline characteristics. All pre-specified covariates will be included in the logistic regression.

The association between ICS prescription and each outcome will be estimated using a Cox regression model to calculate hazard ratios and 95% CIs, using time in study as the time scale. Univariable models, models adjusted for age and sex, and propensity score weighted models will be presented. Schoenfeld residuals will be used to graphically assess the validity of the proportional hazards assumption. If the proportional hazards assumption is violated, we will use interaction terms between the exposure and time to describe any variations in the hazard ratio over time.

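### Section O gives Cox models with 95% CIs but no allowance for grouping by GP practice; intervals for objective 2a, chiefly in asthma, can be too narrow if prescribing and infection both vary between practices

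*Protocol*

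**What the plan says.** Section O (comparative cohort studies) sets the estimator, the interval and the time scale: "using a Cox regression model to calculate hazard ratios and 95% CIs, using time in study as the time scale". It then lists the models: "Univariable models, models adjusted for age and sex, and propensity score weighted models will be presented". It adds Schoenfeld residuals, exposure-by-time interactions if hazards are not proportional, and censoring weights if exposure is time-updated. No section mentions practice as a cluster, stratum, frailty or random effect, and none names the variance estimator.

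The grouping itself is documented. Section H says of the database: "These patients come from over 1,300 GP practices which use EMIS GP patient management software". Section L defines both disease cohorts as "consisting of patients registered with GP practices meeting CPRD quality control standards".

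The nearest adjustments, in section N, are deprivation, ethnicity, calendar time and ONS prevalence figures. The geographical level of the prevalence figures is not given.

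**The concern.** Infection spreads locally, and the choice between ICS and another inhaler may differ from practice to practice. If both vary between practices, patients of one practice resemble each other in exposure and in outcome, and the variance of the log hazard ratio exceeds what an independent-patients formula gives. A sandwich variance computed per patient, as often used with weighted Cox models, does not correct this, because it still treats patients within a practice as independent.

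Section G describes objective 2 as testing hypotheses, so intervals that are too narrow would produce too many false positives. Section P then starts its bias analysis from these estimates. If its simulation intervals carry over the Cox standard error, any understatement goes with it.

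**Working it through.** **The plan's own figure.** Table 1 in section K follows from the Schoenfeld formula, with events D = (1.960 + 0.842)² / (0.64 × 0.36 × ln(HR)²) and N = D / outcome probability. For HR 1.1, D = 3,750.13, and at 0.5% N = 3,750.13 / 0.005 = 750,027, as printed. All 28 cells in the 0.05%, 0.1%, 0.5% and 1.0% rows match. The table therefore carries no design effect.

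**Inputs from the protocol**
- Practices: over 1,300 (section H).
- Asthma: "755,632 patients with an asthma code between 1st March 2017 and 29th February 2020" (section J), so m = 755,632 / 1,300 = 581 per practice.
- COPD: "225,472 patients with a COPD code before 29th February 2020" (section J), so m = 225,472 / 1,300 = 173.
- ICS share q: "Of the patients with asthma, 485,192 had a prescription for ICS", so 485,192 / 755,632 = 64.2%; for COPD 83,668 / 225,472 = 37.1%.
- Wave 1 risks in section K: positive test 0.52%, death 0.065%.

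**Assumed, because the protocol gives no figure**
- Coefficient of variation (CV) of the practice infection rate: 0.3-0.8.
- SD of the practice ICS share: 0-12 percentage points.
- A commoner positive-test risk of 5-6%, standing in for wave 2, for which no rate is given.

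**Formulas**
- Outcome ICC ≈ p × CV² / (1 − p)
- Exposure ICC = SD² / (q(1 − q))
- Design effect (DEFF) ≈ 1 + (m − 1) × exposure ICC × outcome ICC
- Shortfall of the standard error = 1 − 1/√DEFF
- True coverage = 2Φ(1.96/√DEFF) − 1

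**Worked case** (asthma, p = 5%, CV 0.5, SD 10 points): outcome ICC = 0.05 × 0.25 / 0.95 = 0.0132; exposure ICC = 0.01 / (0.642 × 0.358) = 0.0435; DEFF ≈ 1.33. The standard error is 13% too small and coverage is 91%.

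| Cohort | Risk | CV | SD (points) | DEFF | SE too small by | Coverage |
|---|---|---|---|---|---|---|
| Asthma | 0.52% | 0.3 | 5 | 1.003 | 0.1% | 95.0% |
| Asthma | 0.52% | 0.5 | 10 | 1.033 | 1.6% | 94.6% |
| Asthma | 0.52% | 0.8 | 10 | 1.084 | 4.0% | 94.0% |
| Asthma | 5% | 0.3 | 5 | 1.030 | 1.5% | 94.7% |
| Asthma | 5% | 0.5 | 5 | 1.083 | 3.9% | 94.0% |
| Asthma | 5% | 0.5 | 10 | 1.332 | 13.4% | 91.1% |
| Asthma | 6% | 0.5 | 12 | 1.580 | 20.4% | 88.1% |
| COPD | 0.52% | 0.8 | 10 | 1.025 | 1.2% | 94.7% |
| COPD | 5% | 0.5 | 10 | 1.097 | 4.5% | 93.9% |
| Asthma, death | 0.065% | 0.8 | 10 | 1.011 | 0.5% | 94.9% |

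The 4% figure at 0.52% needs a CV of 0.8. With that CV and SD 10 points at 5% risk, the asthma DEFF would be 1.85 and coverage 85%, outside the main range used here.

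**Simulation check** (1,300 practices). Asthma at 5% with CV 0.5: coverage of the ordinary interval is 95.2% with no practice variation in ICS share, 94.2% at SD 5 points and 90.7% at SD 10. Practice-clustered intervals cover 94.8-95.4% in the same runs. A separate simulation at 6%, CV 0.5 and SD 12 points gave a ratio of empirical SD to ordinary standard error of 1.26 and coverage of 87.6%. The shortfall is 1 − 1/1.26 = 21%.

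**Objective 2b.** In wave 1 about 581 × 0.0052 = 3 test-positive asthma patients fall in each practice. Even with assumed ICCs of 0.10 (outcome) and 0.043 (exposure), DEFF = 1 + 2.02 × 0.10 × 0.043 = 1.009. If 5% test positive, about 29 fall in each practice, and DEFF is about 1.01-1.12 across the assumed ICCs.

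**Power.** For asthma and HR 1.1 at 0.52%, 755,632 × 0.0052 = 3,929 events give power 0.82 by the Table 1 formula. This falls to 0.80 at DEFF 1.05 and 0.78 at 1.10.

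**The case against.** The strongest objection is that the protocol never says patients will be treated as independent. It is silent on the variance estimator, which is commonly left to an analysis plan, and none is shown. A reader might infer from section O, or from Table 1, that the analysis will assume independence. Table 1 shows only that the sample size was planned that way. This objection stands, so the point is a provision worth writing in, not a demonstrated error.

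A reader might also infer that the intervals are too narrow as a matter of fact. The documents do not support that, because no section reports how ICS prescribing or infection varies between practices. If the ICS share does not vary, the ordinary interval keeps about 95% coverage.

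The cluster sizes are upper bounds. Cohort members must also "be eligible for linkage to HES data", have no other chronic respiratory condition and meet age limits, and under the time-fixed definition have an inhaler prescription within 3 months. Linkage may reduce the number of practices as well, but the other restrictions reduce patients per practice. At half of 581, the largest table entry (DEFF 1.58) falls to about 1.29, a shortfall of about 12%. The section N covariates may also absorb some area-level correlation, and the calculations above include no covariates.

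Finally, saying that the effect grows with a commoner outcome might be read as pointing to objectives 2b and 2c. For 2b there are too few patients per practice in wave 1 to matter. For 2c nothing was calculated, as the protocol gives no hospitalisation rate.

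**Conclusion.** The point holds conditionally. At the outcome risks the protocol states, the effect is negligible to small. It becomes material only for a common outcome in a large cohort, which means positive tests in asthma, most plausibly in wave 2, and only if prescribing varies by practice. The size at 5-6% risk depends jointly on the assumed risk, CV, SD and cluster size, none of which the documents fix. The simulation ratio of 1.26 should not be read as a standard error 26% too small; it corresponds to about 21%. The consequence for the bias analysis is possible but not shown, since section P does not say how random error enters the simulation intervals. This is a cheap improvement, not a flaw that undermines the design.

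**What to change.** In section O, state that all Cox models, including the weighted ones, use a robust sandwich variance clustered on GP practice. The gain is chiefly for objective 2a. A Cox model stratified by practice can be added for 2a as an optional sensitivity analysis.

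The cost is one sentence and one option in the model code. The downside is slightly wider intervals where clustering is present. In the simulations, coverage stayed near 95% with the clustered variance whether or not practices differed, so little is lost if they do not.

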D. Aims, objectives, rationale

The aim of this study is to investigate the effects of ICS at different stages of the COVID-19 disease pathway (i.e., infection, hospitalisation, and death) among patients with asthma or COPD and apply methods of QBA to these effect estimates to account for potential biases arising in these estimates of association. The null hypothesis is that use of ICS has no effect on COVID-19-related outcomes.

Objectives

- A. To describe prescription patterns of ICS among patients with respiratory diseases before and during the COVID-19 pandemic.
- B. To investigate the association between prevalent ICS use and COVID-19 related outcomes among patients with respiratory diseases.
 - a. Estimate the association between prevalent ICS use and risk of having a positive SARS-CoV-2 test.
 - b. Estimate the association between prevalent ICS use and risk of hospitalization with COVID-19 among patients with a positive SARS-CoV-2 test.
 - c. Estimate the association between prevalent ICS use and risk of death among patients who were hospitalized with COVID-19.
- C. To develop approaches and apply methods of QBA to account for potential biases arising in these estimates of association.
 - a. Investigate impact of exposure misclassification (e.g., due to stockpiling of medication, patients not filling prescription or underascertainment of in-hospital medication use) on estimates from objective 2a, 2b, and 2c.
 - b. Quantify potential biases due to unmeasured or unknown confounders on estimates from objective 2a, 2b, and 2c.
 - c. Investigate impact of outcome misclassification (e.g., underascertainment of infections due to limited testing availability and non-random testing) on estimates from objective 2a.
 - d. Investigate impact of selection bias (e.g., non-random selection of individuals into a study) on estimates from objective 2b and 2c.

E. Outcomes

COVID-19 positive test result; hospitalisation with COVID-19; death with COVID-19, as defined in section N.

F. Study type

The overall study design is a historical cohort study.

G. Study design

Objective 1 will be a descriptive study with a population-level description of prescription patterns of ICS before and during the COVID-19 pandemic among patients with respiratory disease.

Objective 2 will be a hypothesis testing cohort study. The null hypothesis is that there is no association between ICS use and testing positive for COVID-19, hospitalisation for COVID-19 and death with COVID-19.

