If a time-updated exposure definition is used, we will account for potentially informative censoring using inverse-probability of censoring weights. Propensity scores will also be time-updated to account for time-dependent confounding.

A number of sensitivity analyses/additional analyses will be conducted:

- Stratification by ICS dose (low/medium vs higher)
- Do not condition on positive test (2b) or hospitalisation (2c), in order to repeat published analyses

- Include people with a diagnostic code for COVID-19, or a code that implied SARS-CoV-2 infection, but no registered positive SARS-CoV-2 test

P. Quantitative Bias Analysis

Quantitative Bias Analysis Method:

We will use probabilistic bias analysis to quantify the effect of biases on the effect estimates in objectives 2a-c. In probabilistic bias analysis, each bias parameter is assigned a distribution which reflects the uncertainty around the specific value for the parameter. The bias parameters are sampled repeatedly from this distribution and applied to the observed effect measure to obtain a bias-adjusted point estimate and simulation interval.^{22,46} For research questions where more than one bias may have a significant impact, we will also conduct multiple bias modelling to obtain effect estimates that are adjusted for several biases.

Misclassification:

We will use a range of plausible values for sensitivity and specificity of the outcome and exposure classification to adjust for outcome and exposure misclassification, respectively.

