Exposure misclassification may arise due to low adherence to inhaled medication for respiratory diseases⁴⁷⁻⁴⁹, and due to stockpiling of medication⁴⁷ at the beginning of the pandemic (March and April 2020). The descriptive cohort study (objective 1) will investigate prescription patterns and the potential extent of stockpiling during the pandemic. To adjust for potential exposure misclassification, we will calculate proxy measures for adherence (proportion of days covered or medication possession ratio) in the year before the COVID-19 pandemic (March 2019 – February 2020) and use these, together with data from literature and input from clinicians, to estimate adherence during the pandemic. Additionally, we are looking to obtain questionnaire data on adherence during the pandemic from the Optimum Patient Care Research Database (OPCRD). If this data is not obtained, or is not suitable for these purposes, we will estimate exposure misclassification using data from literature and input from clinicians.

In objective 2a, the outcome of SARS-CoV-2 infection may be misclassified as testing was conducted in a non-random manner. Especially in the first wave of COVID-19, testing was very limited, and therefore not all infections will have been ascertained. It is plausible that the probability of getting tested for SARS-CoV-2 was not equal among people prescribed ICS and those not prescribed ICS, resulting in differential misclassification of SARS-CoV-2 infection. We will use test data from CPRD and data from the ONS infection survey to estimate how many SARS-CoV-2 infections may have been missed in the respective study populations. We will work together with clinicians to create plausible bounds for sensitivity and specificity of the outcome classification.

Selection Bias:

Analyses that are restricted to people who received a positive test for SARS-CoV-2 or were hospitalised with COVID-19 may be vulnerable to selection bias. Potential differential misclassification of SARS-CoV-2 infections in objective 2a would result in selection bias in objective 2b, as selection into the study

population is conditional on a positive test for SARS-CoV-2. In order to adjust for selection bias, the bias parameters necessary are the selection probabilities S for each combination of exposure E and outcome D :

- Probability of being selected into the study conditional on being exposed and experiencing the outcome ($P(S|D=1, E=1)$),

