- Probability of being selected conditional on being exposed and not experiencing the outcome ($P(S|D=0, E=1)$),
- Probability of being selected conditional on being unexposed and experiencing the outcome ($P(S|D=1, E=0)$),
- Probability of being selected conditional on being unexposed and not experiencing the outcome ($P(S|D=0, E=0)$).

The observed effect estimate can then be multiplied with the OR for differential selection to give an effect estimate adjusted for differential selection into the study population. To estimate the impact of possible selection bias affecting effect estimates in objective 2b, we will use information relating to the underascertainment of SARS-CoV-2 infections, described above. To account for selection bias in objective 2c, we will use HES data, together with data on ICS exposure from CPRD and data on the outcome, death with COVID-19, from the ONS death registry, to determine probabilities for being selected into the study population (i.e., being hospitalised with COVID-19) for each combination of exposure and outcome.

Confounding:

We expect that there will be unmeasured confounding affecting the effect estimates in objectives 2a-c. A likely key source of unmeasured confounding may be the severity of the underlying respiratory disease. It has not been elucidated completely how asthma and COPD affect COVID-19 outcomes^{7,50-55}, but it is plausible that severity of respiratory disease influenced COVID-19 outcomes and that people using ICS had a different severity of underlying respiratory disease than those not prescribed ICS. Any observed effect of ICS on COVID-19 outcomes may then be partly due to different severity of respiratory disease between the exposed and unexposed. We will account for unmeasured confounding by respiratory disease severity using an estimate of the association between severe respiratory disease and the outcome among the unexposed, an estimate of the association between severe respiratory disease and ICS exposure, and the prevalence of severe respiratory disease among the source population.^{23,56} We will work together with clinicians to develop an algorithm to identify severe respiratory disease in CPRD and/or estimate plausible bounds.

Q. Plans for addressing confounding

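### The selection-bias correction for objectives 2b and 2c applies an odds-ratio factor of undefined orientation to a Cox hazard ratio, so the corrected estimates can be materially wrong

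*Protocol*

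**What the plan says.** Protocol section O sets the effect measure: "The association between ICS prescription and each outcome will be estimated using a Cox regression model to calculate hazard ratios and 95% CIs".

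Section D defines the two conditional analyses. For 2b: "Estimate the association between prevalent ICS use and risk of hospitalization with COVID-19 among patients with a positive SARS-CoV-2 test". For 2c: "Estimate the association between prevalent ICS use and risk of death among patients who were hospitalized with COVID-19".

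Section P describes probabilistic bias analysis in which sampled bias parameters are "applied to the observed effect measure to obtain a bias-adjusted point estimate" and a simulation interval. Under Selection Bias it says that "the bias parameters necessary are the selection probabilities S for each combination of exposure E and outcome D", lists the four probabilities, and then gives the operation: "The observed effect estimate can then be multiplied with the OR for differential selection to give an effect estimate adjusted for differential selection".

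The section does not write out the selection odds ratio in terms of the four probabilities. It states no conversion between hazard ratio and odds ratio, and no rare-outcome condition.

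**The concern.** Multiplying by a ratio of selection probabilities is an identity for odds ratios, because the selection probabilities factor out of the cross-product of the 2x2 table. They do not factor out of a hazard ratio. The two measures are close only when the outcome is rare in the population actually analysed. Conditioning on a positive test or on admission makes admission and death much commoner than in the full cohorts, so the approximation is used where it is weakest.

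Separately, because the odds ratio is not defined, two analysts could follow the sentence and move the estimate in opposite directions.

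Quantitative bias analysis is the purpose of this study, and section B promises recommendations and tools for other researchers. A flawed correction rule could therefore be copied elsewhere.

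**Working it through.** The plan states no figure for this correction, so there is none to reproduce. The check is algebra followed by illustrative numbers.

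**Notation.** Write s11, s01, s10 and s00 for the selection probabilities, with the first index the outcome D and the second the exposure E. So s01 is for exposed people without the outcome. Let K = (s11 × s00) / (s01 × s10).

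**Odds ratio.** Each selected cell is the source cell times its selection probability, so OR_obs = OR_true × K. The exact correction is OR_obs / K, which equals OR_obs × (s01 × s10)/(s11 × s00).

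**Hazard ratio.** With source risk r, the selected risks are p1 = r1·s11 / [r1·s11 + (1 − r1)·s01] and p0 = r0·s10 / [r0·s10 + (1 − r0)·s00]. I approximate HR = ln(1 − p1)/ln(1 − p0), which ignores event timing and covariates. K does not factor out of this unless p1 and p0 are small.

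**Are the outcomes rare?** Section K reports that "295,134 positive SARS-CoV-2 tests were reported in England" in wave 1, and 36,974 deaths with COVID-19. The ratio is 36,974 / 295,134 = 12.5%. It is crude: not every death had a positive test, and it is neither the 2b nor the 2c risk. It does suggest that severe outcomes are not rare once a positive test is required.

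**Main illustration** (assumed): s11 = 0.9, s01 = 0.3, s10 = 0.9, s00 = 0.2, so K = 0.18/0.27 = 0.667. The correction is applied in the right direction, HR_obs / K.

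| Source risk r0 | Selected risk, unexposed | HR_obs, true HR 1.0 | Corrected, true HR 1.0 | Corrected, true HR 1.2 |
|---|---|---|---|---|
| 0.1% | 0.4% | 0.667 | 1.001 | 1.201 |
| 0.5% | 2.2% | 0.669 | 1.004 | 1.203 |
| 2% | 8.4% | 0.676 | 1.014 | 1.213 |
| 5% | 19.1% | 0.690 | 1.035 | 1.230 |
| 12.5% | 39.1% | 0.718 | 1.078 | 1.268 |
| 30% | 65.9% | 0.769 | 1.154 | 1.335 |

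In every row OR_obs / K returns the true odds ratio exactly. If 12.5% is read as a risk among the selected, it falls between the 2% and 5% rows.

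**Error in the other direction** (assumed): true null, 5% risk in both groups, s11 = s10 = 0.9, s01 = 0.05, s00 = 0.075. Then K = 1.5.
- p1 = 0.045/(0.045 + 0.0475) = 0.486 and p0 = 0.045/(0.045 + 0.07125) = 0.387.
- HR_obs = ln(0.514)/ln(0.613) = 1.36, and the corrected value is 1.36/1.5 = 0.91.
- On the odds-ratio scale, 1.5/1.5 = 1.00.

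**Milder differential selection**, true HR 1.2, r0 = 12.5%:
- (s11, s01, s10, s00) = (0.9, 0.5, 0.9, 0.4), K = 0.80: corrected HR 1.221.
- (0.8, 0.3, 0.9, 0.3), K = 0.889: corrected HR 1.201.

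**Selection on outcome only** (assumed): risks 5% and 7.5%, so the true HR is ln(0.925)/ln(0.95) = 1.52. Take s11 = s10 = 0.9 and s01 = s00 = 0.10, 0.05 or 0.02. HR_obs is 1.41, 1.35 or 1.27. K = 1 each time, so the rule leaves the attenuated value as it is.

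**Orientation.** If an analyst multiplies by K, the result is wrong by K². A true OR of 1.0 with K = 1.5 is observed as 1.5 and becomes 2.25. In the 0.91 example the HR becomes 1.36 × 1.5 = 2.04.

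**The case against.** A reader might infer that multiplying is itself the error and that the plan ought to divide. The protocol does not support that. Multiplying by (s01 × s10)/(s11 × s00) is the same as dividing by K, and the sentence's stated aim is an adjusted estimate, which implies the orientation that adjusts. What remains is an undefined term, and a statistical analysis plan might define it.

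A reader might also infer that the 2b and 2c corrections will be wrong. That is too strong. The protocol gives neither selection probabilities nor admission risks, and the error is negligible for rare outcomes and small for mild differential selection. Where selection depends on exposure only, K = 1 and there is no error.

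The outcome-only example can fairly be discounted too. Section P aims at differential selection, and at the null that pattern causes no distortion. It only attenuates a real effect, and its inputs imply that about 32% to 79% of test-positives are admitted, which no section supports.

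Finally, section O plans analyses that do not condition on a positive test or on admission, and the uncorrected hazard ratios are unaffected. Those analyses address a different question and are there to repeat published work.

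These points limit the size of the problem. They do not remove the scale mismatch: the protocol itself states the operation, and its only effect measure for these outcomes is a hazard ratio.

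**Conclusion.** The point holds as a scale mismatch plus an undefined orientation. The stated rule is exact for an odds ratio and approximate for the Cox hazard ratio to which it is applied, and the rarity that the approximation needs is unlikely in 2b and 2c.

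Under strong differential selection, a true hazard ratio of 1.0 is corrected to between 0.91 and 1.15 with the right orientation. With a true value of 1.2 and K = 0.667, the result is 1.268 at 12.5% source risk and 1.335 at 30%, errors of about 6% and 11%. For scale, section K hopes to detect hazard ratios of 1.1 and 1.2, though for testing positive rather than for 2b or 2c. In the main set of assumed values the error is under 0.5% at source risks up to 0.5%.

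All these figures rest on assumed selection probabilities and on the 2x2 approximation. The corrections can therefore be materially wrong, but are not bound to be.

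**What to change.** Replace the sentence in section P, Selection Bias, with one of the following.

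1. Preferred, since it keeps the hazard ratio: in each simulation draw, weight every selected record by 1/P(S|D,E) and refit the weighted Cox model.
2. Alternatively, estimate an odds ratio from a logistic model for the bias-adjusted analysis, and multiply it by [P(S|D=0,E=1) × P(S|D=1,E=0)] / [P(S|D=1,E=1) × P(S|D=0,E=0)], with that expression written out.

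Dividing the four cell counts by their selection probabilities is acceptable for an odds ratio or a risk ratio. It cannot give a corrected hazard ratio, because cell counts carry no event times.

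The cost is one rewritten paragraph, with slightly more code and computing. Either route uses the four selection probabilities that the section already requires.
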